7.0 TREATMENT PLAN/INTERVENTION

Protocol treatment is to begin ≤ 7 days from registration.

Patients are permitted to have a new cycle of treatment delayed up to 7 days for major life events (e.g., serious illness in a family member, major holiday, vacation that cannot be rescheduled) without this being considered a protocol violation. Documentation to justify this delay should be provided.

Patients will receive efatutazone, 0.5mg orally twice daily. Each cycle is 21 days (3 weeks).

If at reimaging there is no evidence of disease progression, and the patient is tolerating therapy, then the patient will continue to remain on treatment until progression.

A091202 dose table:

Agent	Dose	Route	Day	ReRx
Efatutazone	0.5 mg	PO	BID	Every 21 days*

*Taken continuously with no break between cycles

Efatutazone tablets are to be self-administered PO BID, with or without food. The intended dosing schedule for efatutazone dosing is every 12 hours. However, dosing may occur within ± 2 hours of the scheduled administration time.

Treatment is to continue until disease progression or unacceptable adverse event. After disease progression or unacceptable adverse event, patients will be followed for a maximum of 5 years, as in [Section 5.0](#).

8.0 DOSE AND TREATMENT MODIFICATIONS, UNBLINDING

8.1 Ancillary therapy, concomitant medications, and supportive care

8.1.1 Patients should not receive any other agent which would be considered treatment for the primary neoplasm or impact the primary endpoint.

8.1.2 Patients should receive full supportive care while on this study. This includes blood product support, antibiotic treatment, and treatment of other newly diagnosed or concurrent medical conditions. All blood products and concomitant medications such as antidiarrheals, analgesics, and/or antiemetics received from the first day of study treatment administration until 30 days after the final dose will be recorded in the medical records.

8.1.3 Treatment with hormones or other chemotherapeutic agents may not be administered except for steroids given for adrenal failure; hormones administered for non-disease-related conditions (e.g., non-TZD oral agents for diabetes).

8.1.4 Antiemetics may be used at the discretion of the attending physician.

8.1.5 Palliative radiation therapy: Patients who require radiation therapy during protocol treatment will be removed from protocol therapy due to disease progression.

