3.1 On-Study Guidelines

This clinical trial can fulfill its objectives only if patients appropriate for this trial are enrolled. All relevant medical and other considerations should be taken into account when deciding whether this protocol is appropriate for a particular patient. Physicians should consider the risks and benefits of any therapy, and therefore only enroll patients for whom this treatment is appropriate.

Although they will not be considered formal eligibility (exclusion) criteria, physicians should recognize that the following may seriously increase the risk to the patient entering this protocol:

- Psychiatric illness which would prevent the patient from giving informed consent.
- Medical condition such as uncontrolled infection (including HIV), uncontrolled diabetes mellitus or cardiac disease which, in the opinion of the treating physician, would make this protocol unreasonably hazardous for the patient.
- Patients with a “currently active” second malignancy other than non-melanoma skin cancers. Patients are not considered to have a “currently active” malignancy if they have completed therapy and are free of disease for ≥ 3 years.
- Patients who cannot swallow oral formulations of the agent(s).
- Patients with a life expectancy < 12 weeks
- Diabetic patients using insulin therapy are excluded from enrollment unless they are able to discontinue insulin use (in exchange, for example, for non-insulin antihyperglycemic medications) due to the risk of dangerous and rapid fluid retention with the concurrent use of insulin and efatutazone (see [Section 3.3.7](#))

In addition:

- Women and men of reproductive potential should agree to use an appropriate method of birth control throughout their participation in this study due to the teratogenic potential of the therapy utilized in this trial. Appropriate methods of birth control include abstinence, oral contraceptives, implantable hormonal contraceptives or double barrier method (diaphragm plus condom).
- Efaturazone is metabolized by CYP3A4/5, and inhibits CYP2C8, 2C9, 2C19, and 3A4, and is a substrate of Pgp and BCRP. The clinical significance of any drug interactions is unknown to date.

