3.3 Registration/Randomization Eligibility Criteria

3.3.1 Measurable disease as defined in [Section 11.0](#).

3.3.2 Prior Treatment:

Progression on at least one prior systemic chemotherapy for advanced, unresectable or metastatic disease. Prior adjuvant or neoadjuvant therapy is not included as prior systemic chemotherapy unless treatment occurred within the 6 months prior to study enrollment.

- There is no limit to the number of prior lines of treatment a patient has received.
- No treatment with biologic therapy, immunotherapy, chemotherapy, investigational agent for malignancy, or radiation ≤ 28 days before study registration. No treatment with nitrosourea or mitomycin ≤ 42 days before study registration.
- Patients should have resolution of any toxic effects of prior therapy (except alopecia) to NCI CTCAE, Version 4.0, grade 1 or less.

3.3.3 No history of the following:

- Class III or IV congestive heart failure (CHF).
- Pericardial effusion ≤ 12 months (Grade 3 or 4).
- Pericardial involvement with tumor.
- Grade 2 or higher pleural effusion ≤ 6 months.

3.3.4 No symptomatic, untreated, or uncontrolled brain metastases present.

3.3.5 Not pregnant and not nursing, **because this study involves an investigational agent whose genotoxic, mutagenic and teratogenic effects on the developing fetus and newborn are unknown.** Therefore, for women of childbearing potential only, a negative pregnancy test done ≤ 7 days prior to registration is required. A female of childbearing potential is a sexually mature female who: 1) has not undergone a hysterectomy or bilateral oophorectomy; or 2) has not been naturally postmenopausal for at least 12 consecutive months (i.e., has had menses at any time in the preceding 12 consecutive months).

___ **3.3.6 Concomitant medications:**

- Patients with diabetes mellitus requiring concurrent treatment with insulin or thiazolidinedione (TZD) oral agents are not eligible.
- Patients with known hypersensitivity to any TZD oral agents are not eligible.

___ **3.3.7 Age \geq 18 years**

___ **3.3.8 ECOG Performance Status 0-2**

___ **3.3.9 Required Initial Laboratory Values:**

Absolute Neutrophil Count (ANC)	$\geq 1,000/\text{mm}^3$
Platelet Count	$\geq 75,000/\text{mm}^3$
Creatinine	$\leq 1.5 \text{ mg/dL}$ x upper limits of normal (ULN)
OR	
Calc. Creatinine Clearance	$\geq 30 \text{ mL/min}^{**}$
Bilirubin ≤ 1.5 x upper limits of normal (ULN)	
SGOT (AST) and SGPT (ALT)	≤ 2.5 x upper limits of normal (ULN) *

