8.1.6 Alliance Policy Concerning the Use of Growth Factors

Blood products and growth factors should be utilized as clinically warranted and following institutional policies and recommendations. The use of growth factors should follow published guidelines of the American Society of Clinical Oncology 2006 Update of Recommendations for the Use of White Blood Cell Growth Factors: An Evidence-Based, Clinical Practice Guideline. *J Clin Oncol* 24(19): 3187-3205, 2006.

Darbepoietin or Epoetin (EPO): Use of darbepoietin or epoetin in this protocol is permitted at the discretion of the treating physician.

Filgrastim (G-CSF) and sargramostim (GM-CSF)

Filgrastim/pegfilgrastim and sargramostim may not be used:

- a. To avoid dose reductions or delays.
- b. For the treatment of febrile neutropenia the use of CSFs should not be routinely instituted as an adjunct to appropriate antibiotic therapy. However, the use of CSFs may be indicated in patients who have prognostic factors that are predictive of clinical deterioration such as pneumonia, hypotension, multi-organ dysfunction (sepsis syndrome) or fungal infection, as per the ASCO guidelines. Investigators should therefore use their own discretion in using the CSFs in this setting. The use of CSF (filgrastim/pegfilgrastim or sargramostim) must be documented and reported.
- c. If filgrastim/pegfilgrastim or sargramostim are used, they must be obtained from commercial sources.

8.1.7 Hyperlipidemia: Elevations of lipids is a known side effect of this medication. The use of medications for hyperlipidemia is permitted at the discretion of the treating physician.

8.1.8 Anemia: Patients have developed anemia associated with efatutazone. Full supportive care should be utilized at the discretion of the treating investigator.

8.1.9 Edema: Edema/fluid retention is a common side effect of this medication. Patients should maintain the weight diary, and should be weighed with all visits. Patients should contact

their physician with a weight gain of over 5lb. for further management. The following is a suggested regimen for fluid retention but is NOT required:

- With weight gain of 5 lbs. or more, start furosemide 20mg daily and spironolactone 25mg daily
- For additional weight gain unresponsive to initial diuretics, increase dose of furosemide to 40mg daily and spironolactone to 50mg daily

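### Section 3.1 warns against insulin with efatutazone, but the on-treatment hormone exemption in 8.1.3 literally admits insulin, and 8.1, 8.2 and 10.1 never name it

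*Combined protocol and SAP*

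**What the plan says.** **At entry.** Section 3.3.6 states: "Patients with diabetes mellitus requiring concurrent treatment with insulin or thiazolidinedione (TZD) oral agents are not eligible". The schema repeats this rule. Section 3.1 adds a route in and a reason. The route is "Diabetic patients using insulin therapy are excluded from enrollment unless they are able to discontinue insulin use", for example by changing to other glucose-lowering drugs. The reason is "due to the risk of dangerous and rapid fluid retention with the concurrent use of insulin and efatutazone". The list in 3.1 is introduced as advice and not as formal exclusion criteria, so the binding rule is 3.3.6, which gives no reason of its own.

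**On treatment.** Section 8.1.3 begins with a ban: "Treatment with hormones or other chemotherapeutic agents may not be administered". It then makes exceptions: "except for steroids given for adrenal failure; hormones administered for non-disease-related conditions (e.g., non-TZD oral agents for diabetes"). Section 8.1.2 asks for full supportive care, including "treatment of other newly diagnosed or concurrent medical conditions", with no exception for insulin.

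**Elsewhere in the treatment sections.** Insulin is not named in the rest of 8.1 (including the edema advice in 8.1.9), in the dose rules of 8.2, or in 10.1 (Drug Interactions, Adverse Events and the nursing guidelines).

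**The concern.** A hazard of concurrent use lasts as long as dosing lasts, and efatutazone is given continuously until progression or unacceptable toxicity. Eligibility is checked once. After registration, a site deciding whether a drug may be given will look in 8.1, where the relevant sentence can be read either way.

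Two patients are foreseeable. One stopped insulin in order to enrol and later loses glucose control on the substitute drugs. The other develops diabetes during treatment. A site that follows 8.1.2 and the literal exemption in 8.1.3 could give insulin alongside efatutazone and believe that it had complied. What is at stake is the safety of a small number of patients, through a combination that the protocol itself describes as dangerous.

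**Working it through.** No arithmetic decides this point. The check is a comparison of texts.

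1. **Which drugs are restricted at entry?** Two: insulin and TZDs (3.3.6 and the schema).

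2. **Which of them does the on-treatment rule restrict by name?** Only TZDs, and only indirectly, because the example in 8.1.3 is confined to oral agents that are not TZDs. Insulin is not named.

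3. **Does the opening ban in 8.1.3 cover insulin?** Yes. Insulin is a hormone.

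4. **Does the exemption release it?** On the literal words, yes. The exemption covers hormones given for a condition other than the cancer under study, and diabetes is such a condition. The oral-agent example is introduced as an illustration, so it does not close the class. It is also a poor illustration, because oral diabetes drugs are not generally hormones. That makes it harder to tell what the drafters meant to allow.

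5. **Does the example point the other way?** Yes. Limiting it to oral, non-TZD drugs matches the two classes excluded in 3.3.6. The likely intent is therefore that insulin stays barred. Steps 4 and 5 conflict, and that conflict is the ambiguity.

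6. **Does other treatment-phase text settle it?** In the text supplied, insulin appears only in the schema, the PPAR background (1.2.1 and 1.2.4), 3.1 and 3.3.6. Drug Interactions in 10.1 deals with CYP enzymes, ketoconazole, food, gastric pH and transporters. The consent pages, most of Appendix II and the Investigator's Brochure (referred to in 9.3) are not available, so advice there cannot be excluded.

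7. **What limits the harm if the combination is given?**
   - Section 3.3.3 excludes patients with a history of "Class III or IV congestive heart failure (CHF"), recent effusions above stated grades, or pericardial tumor.
   - Weight is taken at scheduled visits, including weeks 2 and 3 of Cycle 1.
   - Section 8.1.9 has the weight diary and the 5-lb call rule.
   - Sections 8.2.2 to 8.2.4 hold, reduce or stop efatutazone for edema and effusions.
   - Section 9.1 solicits limb edema, weight gain and effusions.

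   The exclusions lower the risk. The other measures act once fluid has begun to accumulate. None bars the combination. From Cycle 5, scheduled visits fall on odd cycles only, nominally 2 × 21 = 42 days apart. Between visits, detection rests on the patient's diary and call.

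8. **Is the primary endpoint touched?** No. Under 13.2, every eligible patient who is registered and starts treatment is evaluable. A patient who later stops efatutazone because of insulin stays in the analysis.

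**The case against.** The best answer is that a sensible reader already knows the rule. Section 3.1 speaks of concurrent use, 3.3.6 is headed as a concomitant-medication criterion, and 8.1.3 starts from a ban whose only diabetes example leaves insulin out. A site that had a patient stop insulin to enrol did so under that very warning. Much of this stands: intent is fairly clear, and many investigators would avoid the combination. It does not remove the defect, because the sentence that governs treatment, followed as written, permits what 3.1 warns against.

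A reader might also infer more than the documents support:

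- **That the protocol chose to allow insulin.** It did not. The example in 8.1.3 points the other way.
- **That nothing says what to do if insulin becomes unavoidable.** Section 12.3 supplies a general default. Where the protocol's constraints would harm the patient, protocol therapy stops, the reason is recorded and follow-up continues.
- **That 8.1.6 shows how 8.1 words an outright ban.** The phrase "Filgrastim/pegfilgrastim and sargramostim may not be used" introduces conditions, and the items under it leave room for discretionary use. It is not a model for an absolute prohibition.
- **That high glucose is bound to appear.** Section 5.0 schedules glucose tests, but testing does not make a rise likely. Section 1.2 describes this drug class as insulin-sensitizing, and 10.1 does not list hyperglycemia among the adverse reactions.
- **That the risk can be put as a percentage.** One could assume a rate of insulin need and apply it to 28 patients. That would give the chance that someone needs insulin. Harm also requires a site to take the literal reading, overlook 3.1 and continue efatutazone, and the documents support no figure for those steps.

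**Conclusion.** The point holds as a wording gap with a patient-safety consequence. The hazard is the protocol's own, the literal exemption in 8.1.3 admits the hazardous drug, and no available text in 8.1, 8.2 or 10.1 corrects it.

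The number of patients affected is unknown and probably small. The ceiling is the 28 efatutazone-treated patients in 13.5, already screened against requiring insulin. The 55% peripheral edema in Phase I (1.4.2) is background for efatutazone. No insulin co-exposure is reported there, so it does not measure this interaction. The two-stage design, the evaluable set and the response endpoint are unaffected.

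The conclusion assumes that sites take their on-treatment rules from section 8.1, and that the unavailable texts do not already state the prohibition. If the Investigator's Brochure does state it, the risk is lower, but 8.1.3 should still agree with it. This is a worthwhile clarification at almost no cost, not a fault in the design.

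**What to change.** - **8.1.3.** Take the diabetes example out of the hormone exemption and add a separate sentence: *Insulin and TZDs are prohibited while the patient receives efatutazone; diabetes may be treated with non-insulin, non-TZD agents.*
- **10.1, Drug Interactions.** Repeat this in one line.
- **If insulin becomes unavoidable.** Refer to 12.3: discontinue protocol therapy, document the reason and continue follow-up. Whether a temporary hold is acceptable instead is a clinical judgement for the sponsor. Any hold would fall under the 21-day limit in 8.2.
- **Clerical.** The cross-reference in 3.1 to 3.3.7 leads to the age criterion. It should read 3.3.6.

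The cost is one or two sentences and one line, with no added visits, data items or patients. The downside is that a rare patient who needs insulin, possibly one who is responding, may lose efatutazone.

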8.1.6 Alliance Policy Concerning the Use of Growth Factors

Blood products and growth factors should be utilized as clinically warranted and following institutional policies and recommendations. The use of growth factors should follow published guidelines of the American Society of Clinical Oncology 2006 Update of Recommendations for the Use of White Blood Cell Growth Factors: An Evidence-Based, Clinical Practice Guideline. *J Clin Oncol* 24(19): 3187-3205, 2006.

Darbepoietin or Epoetin (EPO): Use of darbepoietin or epoetin in this protocol is permitted at the discretion of the treating physician.

Filgrastim (G-CSF) and sargramostim (GM-CSF)

Filgrastim/pegfilgrastim and sargramostim may not be used:

- a. To avoid dose reductions or delays.
- b. For the treatment of febrile neutropenia the use of CSFs should not be routinely instituted as an adjunct to appropriate antibiotic therapy. However, the use of CSFs may be indicated in patients who have prognostic factors that are predictive of clinical deterioration such as pneumonia, hypotension, multi-organ dysfunction (sepsis syndrome) or fungal infection, as per the ASCO guidelines. Investigators should therefore use their own discretion in using the CSFs in this setting. The use of CSF (filgrastim/pegfilgrastim or sargramostim) must be documented and reported.
- c. If filgrastim/pegfilgrastim or sargramostim are used, they must be obtained from commercial sources.

8.1.7 Hyperlipidemia: Elevations of lipids is a known side effect of this medication. The use of medications for hyperlipidemia is permitted at the discretion of the treating physician.

8.1.8 Anemia: Patients have developed anemia associated with efatutazone. Full supportive care should be utilized at the discretion of the treating investigator.

8.1.9 Edema: Edema/fluid retention is a common side effect of this medication. Patients should maintain the weight diary, and should be weighed with all visits. Patients should contact

their physician with a weight gain of over 5lb. for further management. The following is a suggested regimen for fluid retention but is NOT required:

- With weight gain of 5 lbs. or more, start furosemide 20mg daily and spironolactone 25mg daily
- For additional weight gain unresponsive to initial diuretics, increase dose of furosemide to 40mg daily and spironolactone to 50mg daily
- For patients allergic to sulfa-containing drugs where there may be concern over the use of furosemide, bumetanide may be used in place of furosemide at doses of 1mg daily, and increased to 2 mg daily, as needed for weight gain unresponsive to initial diuretics.

8.2 Dose Modifications

General rules for dose modification:

- If multiple adverse events are seen, administer dose based on greatest reduction required for any single adverse event observed. Reductions or increases apply to treatment given in the preceding cycle and are based on adverse events observed since the prior dose.
- Efatutazone will not be re-escalated once reduced
- If dose reductions beyond dose level -2 is required or efatutazone is held for 21 days, efatutazone will be discontinued.

CTEP-AERS reporting may be required for some adverse events (See [Section 9.0](#))

8.2.1 Dose Levels

Dose Level	Drug Name	Dose
0*	Efatutazone	0.5 mg BID
-1	Efatutazone	0.5 mg every morning, 0.25mg every evening
-2	Efatutazone	0.25 BID

*Dose level 0 refers to the starting dose.

8.2.2 Cardiac Toxicity

For **grade 3 or 4 pericardial effusion**, discontinue efatutazone

8.2.3 General disorders

- For **grade 2 edema**, omit efatutazone until grade < 2, then resume efatutazone at same dose with diuretic support
- For **grade 3 edema**, omit efatutazone until grade < 2, then resume efatutazone at one dose level decreased with diuretic support

8.2.4 Pulmonary Toxicity

- For **grade 2 pleural effusion**, omit efatutazone until grade \leq 1, then resume efatutazone at one dose decreased with diuretic support
- For **grade 3 or 4 pleural effusion**, discontinue efatutazone with diuretic support

8.2.5 Metabolism and nutrition disorders

For **grade 3 or 4 hypertriglyceridemia** that has physiologic or life-threatening consequences, omit efatutazone until physiologic or life-threatening consequences have resolved, then resume at same dose. If grade 3 or 4 hypertriglyceridemia is based on the numeric value and there are no physiologic or life-threatening consequences, do not interrupt drug.

8.2.6 Non-hematologic Toxicities

For all other **grade 3 or 4 non-hematologic toxicities** likely related to efatutazone, omit efatutazone until resolved to \leq grade 1, then resume efatutazone at one dose decreased

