1.4 Efatutazone (CS-7017, Daiichi-Sankyo)

1.4.1 Pre-clinical Data

Efatutazone is a novel, third-generation thiazolidinedione that selectively activates PPAR γ -mediated transcription, with little effect on other PPAR subtypes. Efatutazone is ≥ 50 -times more potent than rosiglitazone and 500-times more potent than troglitazone at PPAR response element-activation and inhibition of cancer cell growth [46]. Efatutazone inhibits proliferation of human pancreatic and anaplastic thyroid tumor-cell cultures, as well as growth of human colorectal tumor xenografts in nude rodents [47]. The antitumor activity of efatutazone *in vivo* may be enhanced in combination with cytotoxic agents including gemcitabine, paclitaxel, and irinotecan [48].

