9.2 CTCAE Routine Study Reporting Requirements

***Combinations of CTCAE Grade & Attribution Required for Routine AE Data Submission on Case Report Forms (CRFs)**

Attribution	Grade 1	Grade 2	Grade 3	Grade 4	Grade 5
Unrelated			a	a	a
Unlikely			a	a	a

Possible		a	a, b	a, b	a, b
Probable		a	a, b	a, b	a, b
Definite		a	a, b	a, b	a, b

- a) Adverse Events: Other CRF - Applies to AEs occurring between registration and within 30 days of the patient's last treatment date, or as part of the Clinical Follow-Up Phase.
- b) Adverse Events: Late CRF - Applies to AEs occurring greater than 30 days after the patient's last treatment date.

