13.6 AE Stopping Rule

The stopping rule specified below is based on the knowledge available at study development. We note that the Adverse Event Stopping Rule may be adjusted in the event of either (1) the study re-opening to accrual after any temporary suspension or (2) at any time during the conduct of the trial and in consideration of newly acquired information regarding the adverse event profile of the treatment(s) under investigation. The study team may also choose to suspend accrual because of unexpected adverse event profiles that have not crossed the specified rule below.

Accrual will be temporarily suspended to this study if at any time we observe events considered at least possibly related to study treatment (i.e., an adverse event with attribute specified as "possible", "probable", or "definite") that satisfy any of the following criteria:

- If at any time, 3 of the initial 9 treated patients or 33% or more of all patients (i.e. when accrual is greater than 9 patients) have experienced a grade 4 adverse event.
- If at any time, 2 patients have experienced a grade 5 adverse event (not due to progressive disease).

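### Section 8.2.6 has no hypersensitivity exception, so its written default after a recovered, drug-related Grade 3-4 allergic reaction is to restart efatutazone

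*Combined protocol and SAP*

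**What the plan says.** Section 8.2 of the protocol sets dose rules by event. Sections 8.2.2 to 8.2.5 deal with pericardial effusion, edema, pleural effusion and hypertriglyceridemia. Section 8.2.6 takes every remaining Grade 3 or 4 non-hematologic toxicity that is "likely related to efatutazone, omit efatutazone until resolved to" at most "grade 1, then resume efatutazone at one dose decreased".

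Level -1 in Section 8.2.1 is "0.5 mg every morning, 0.25mg every evening". The general limit in Section 8.2 reads: "If dose reductions beyond dose level -2 is required or efatutazone is held for 21 days, efatutazone will be discontinued".

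At entry, Section 3.3.6 states: "Patients with known hypersensitivity to any TZD oral agents are not eligible". Section 1.4.1 places the study drug in that class: "Efatutazone is a novel, third-generation thiazolidinedione".

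Two general clauses also bear on the point. Section 7.0 continues treatment while the patient tolerates it and ends it for an unacceptable adverse event. Section 12.3 requires discontinuation if keeping to the protocol would harm the patient.

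**The concern.** A patient who has had a severe allergic reaction to efatutazone is now known to be hypersensitive to a TZD, which is the characteristic that bars entry. The dosing section nevertheless handles the event like any other severe toxicity: wait for recovery, go down one level, restart. Dose reduction is a natural answer to a dose-related toxicity such as fluid retention. It is a weak one to an allergic reaction, and here the reduction leaves the morning dose as it was.

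What is at stake is the safety of an individual patient at rechallenge. A site that looks up the dose rule for this event finds an instruction to resume. To avoid re-exposure, someone has to set that instruction aside under a general clause. The two-stage design, its decision rules and the response endpoint are not affected.

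**Working it through.** No figure in the plan needs reproducing. The check is a reading of the rules, plus dose arithmetic from Section 8.2.1.

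**Step 1: which events have their own rule.**

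- Section 8.2.2, Grade 3-4 pericardial effusion: discontinue.
- Section 8.2.3, Grade 2 edema: hold, then resume at the same dose. Grade 3 edema: hold, then resume one level lower.
- Section 8.2.4, Grade 2 pleural effusion: hold, then resume one level lower. Grade 3-4: discontinue.
- Section 8.2.5, Grade 3-4 hypertriglyceridemia: hold only if there are physiologic or life-threatening consequences, then resume at the same dose.
- Section 8.2.6, everything else that is Grade 3-4, non-hematologic and likely drug-related: hold, then resume one level lower.

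The only permanent stops tied to an event are the two for effusions. A Grade 3-4 allergic reaction judged likely drug-related falls to Section 8.2.6.

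**Step 2: whether a hypersensitivity rule sits elsewhere.** Hypersensitivity appears in the schema and in Section 3.3.6, both times as an entry exclusion. Allergy appears in Section 8.1.9, where it concerns sulfa drugs and the choice of diuretic. Sections 7.0, 9, 10.1 and 12 contain no on-treatment rule for an allergic reaction to efatutazone.

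**Step 3: apply the rule as written to a patient at the starting dose.**

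- Level 0: 0.5 + 0.5 = 1.0 mg per day.
- First reaction: hold. If it recovers to Grade 1 or less before the hold reaches 21 days, resume at level -1: 0.5 + 0.25 = 0.75 mg per day, and 0.75 / 1.0 = 75% of the starting daily dose. The morning dose is 0.5 / 0.5 = 100% of the starting single dose; the evening dose is 0.25 / 0.5 = 50%.
- Second reaction, same conditions: resume at level -2: 0.25 + 0.25 = 0.5 mg per day, or 50%.
- Third reaction: a further reduction would go below level -2, so Section 8.2 discontinues.

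One re-exposure follows from a single reaction. Two is the ceiling; it needs both holds to end before 21 days and nobody to invoke Section 7.0 or 12.3.

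**Step 4: compare with the entry rule.** Section 3.3.6 keeps out anyone with known hypersensitivity to any TZD, and Section 1.4.1 makes efatutazone a TZD. A patient barred at the door for this reason would, if the reaction first showed itself on study, be restarted under the dosing rule. There is no textual contradiction, because Section 3.3.6 governs entry only. The mismatch lies in how the two rules treat the same hazard.

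**Step 5: how often.** Section 13.5 plans for up to 25 + 3 = 28 efatutazone-treated patients. No document gives a hypersensitivity rate for efatutazone, and the reactions listed in Section 10.1 do not include it. Even an assumed rate would give only the chance of a reaction, not of a reaction followed by re-dosing. No probability is offered.

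**The case against.** The strongest reply is that Section 8.2.6 is not read alone. Section 7.0 ends treatment for an unacceptable adverse event. Section 12.3 is mandatory and overrides the protocol's own rules when following them would harm the patient. General clauses exist to cover events nobody named. Section 9.3 also requires the Study Chair, the central protocol office and the IRB to be told of any event needing expedited reporting, on a 24-hour clock for Grade 4 and within 10 calendar days for Grade 3. Most of this stands: the site has clear grounds to stop and is not acting unseen. But the general clauses do not name the event, the reporting duty is not a dosing rule, and the rule that does address dosing points to resumption.

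Second, the event is hypothetical in these documents. Section 10.1 draws on 10 completed studies and does not list it; nor do the solicited events in Section 9.1. That stands, and it keeps the point minor.

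Third, Section 3.3.6 gives no reason for the exclusion and no grade threshold, so reading it as protection against re-exposure is an inference. That also stands. The fix is confined to Grade 3-4 because that is where Section 8.2.6 supplies a default to resume.

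Fourth, the Investigator's Brochure may give rechallenge advice. It is not among the documents, and Section 8.2 does not refer to it, so this cannot be settled.

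**Conclusion.** The gap is real and small. For a likely drug-related Grade 3-4 allergic reaction that recovers in under 21 days, the written default is to restart at 75% of the daily dose with an unchanged morning dose. This assumes that hypersensitivity counts as a non-hematologic toxicity under Section 8.2.6 and that no unseen document overrides it. It is a patient-safety point only.

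Three stronger readings may tempt a reader.

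- *The protocol compels rechallenge.* It does not: Sections 7.0 and 12.3 permit or require stopping.
- *The phrase about likely relatedness should be replaced throughout Section 8.2.6*, because the attribution codes in Section 9.2 (the table headed "Combinations of CTCAE Grade & Attribution Required for Routine AE Data Submission") contain no such category. The mismatch exists, but moving the whole rule to possible, probable or definite would force holds and reductions for every possibly related Grade 3-4 toxicity. Section 8.2 bars re-escalation, so dose intensity could fall in a response-rate trial. That is a separate decision.
- *A permanent stop is also owed for severe heart failure.* The effusion rules support this only by analogy, and the documents do not establish it.

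**What to change.** Add one line to Section 8.2, for example: *For a Grade 3 or 4 hypersensitivity or allergic reaction, or anaphylaxis, with attribution possible, probable or definite, discontinue efatutazone permanently.* State in Section 8.2.6 that this event is exempt.

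The attribution threshold follows Section 13.6, which counts "events considered at least possibly related to study treatment". Using it for this one event avoids any dispute over what likely relatedness means, and leaves the threshold for all other toxicities unchanged.

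The cost is a short amendment with no extra visits, tests or patients. The downside is that a few patients whose reaction was only possibly due to efatutazone lose the option of re-dosing after recovery.
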